8.4. Emergency Unblinding of Treatment Assignment

Not applicable.

8.5. Adverse Events of Special Interest

Specific AEs, or groups of AEs, will be followed as part of standard safety monitoring activities.

- ALT $\geq 5 \times$ ULN
- AST $\geq 5 \times$ ULN
- Colitis
- Diarrhea Grade ≥ 2
- Intestinal perforation
- Rash Grade ≥ 2
- Exfoliative dermatitis
- Pneumonitis
- PJP infection
- CMV infection
- Herpes simplex virus infection
- Varicella zoster virus infection

8.6. Pregnancy

Pregnancy, in and of itself, is not regarded as an AE unless there is suspicion that study drug may have interfered with the effectiveness of a contraceptive medication or method. When a pregnancy has been confirmed in a subject during maternal or paternal exposure to study drug, the following procedures should be followed in order to ensure subject safety:

- The study drug must be discontinued immediately (female subjects only; see Section 5.4.1 for the maximum permitted duration of study drug interruption).
- The investigator must complete and submit the Incyte Clinical Trial Pregnancy form to the sponsor or its designee within **24 hours** of learning of the pregnancy.

Data on fetal outcome and breastfeeding are collected for regulatory reporting and drug safety evaluation. Follow-up should be conducted for each pregnancy to determine outcome, including spontaneous or voluntary termination, details of the birth, and the presence or absence of any birth defects, congenital abnormalities, or maternal and/or newborn complications, by following until the first well-baby visit. Pregnancy should be recorded on a Clinical Trial Pregnancy form and reported by the investigator to the sponsor or its designee. Pregnancy follow-up information should be recorded on the same form and should include an assessment of the possible causal relationship to the sponsor's study drug to any pregnancy outcome, as well as follow-up to the first well-baby visit or the duration specified in local regulations, whichever is later. Refer to the Incyte Reference Guide for Completing the Clinical Trial Pregnancy Form.

Any SAE occurring during pregnancy must be recorded on the SAE report form and submitted to the sponsor or designee.

8.7. Warnings and Precautions

Special warnings or precautions for the study drug, derived from safety information collected by the sponsor or its designee, are presented in the **IB**. Additional safety information collected between IB updates will be communicated in the form of Investigator Notifications (INs). Any important new safety information should be discussed with the subject during the study, as necessary. If new significant risks are identified, they will be added to the ICF.

8.8. Independent Data Monitoring Committee

An IDMC will be formed and will consist of qualified individuals who are not involved with the conduct of the study. The establishment, composition, roles, duties, and responsibilities of the IDMC are addressed in the approved IDMC charter.

8.9. Product Complaints

The sponsor collects product complaints on study drugs and drug delivery systems used in clinical studies in order to ensure the safety of study participants, monitor quality, and facilitate process and product improvements.

All product complaints associated with material packaged, labeled, and released by the sponsor or its designee will be reported to the sponsor. All product complaints associated with other study material will be reported directly to the respective manufacturer.

The investigator or his/her designee is responsible for reporting a complete description of the product complaint via email or other written communication to the sponsor contact or respective manufacturer as noted in the packaging information. Any AE associated with a product complaint should be reported as described in Section **8.1.2** of this Protocol.

[figure not shown]
If the investigator is asked to return the product for investigation, he/she will return a copy of the product complaint communication with the product.

9. STATISTICS

9.1. Study Populations

The full analysis set includes all subjects enrolled in the study who received at least 1 dose of INCB050465. The full analysis set will be used for the summary of demographics, baseline characteristics, subject disposition, and analyses of all efficacy data.

The safety population includes the same set of subjects as the full analysis set. This population will be used for all safety analyses.

9.2. Selection of Sample Size

- Cohort 1: Up to 90 subjects were planned to be enrolled. If the true ORR is 28%, then there is approximately 90% or 96% probability of observing the lower bound of the 95% CI of $ORR \geq 12\%$ with 60 or 90 subjects, respectively. Cohort 1 will be closed to further enrollment by Protocol Amendment 7 with approximately 50 subjects enrolled.
- Cohort 2: Up to 100 subjects will be enrolled. If the true ORR is 60%, then there is approximately 90% or 97% probability of observing the lower bound of the 95% CI of $ORR \geq 40\%$ with 60 or 100 subjects, respectively.

9.3. Level of Significance

There will not be any statistical comparison between Cohort 1 and Cohort 2. Within each of the 2 cohorts, 2-sided 95% CIs will be reported for all analyses when appropriate.

9.4. Statistical Analyses

All analyses will be conducted independently for Cohort 1 and Cohort 2, and there will not be multiplicity adjustment between the cohorts.

Within each of the 2 cohorts, efficacy data from the 2 treatment regimens (A and B) will be combined for the purpose of the primary and secondary efficacy analyses. Safety data will be summarized by treatment regimen and combined.

9.4.1. Efficacy Analyses

9.4.1.1. Primary Efficacy Analyses

Objective response rate is defined as the percentage of subjects with a CR or PR as determined by revised response criteria for lymphomas (Cheson et al 2014).

The ORR as determined by the IRC and its 95% exact binomial CIs will be calculated. This is considered the primary efficacy analysis for each of the 2 cohorts.

The ORR as reported by the investigator and its 95% exact binomial CIs will also be calculated.

Response data will be analyzed when all subjects in the full analysis set of the respective cohort have reached at least 1 postbaseline disease assessment or have progressed, withdrawn from the study, or died.

9.4.1.2. Secondary Efficacy Analyses

Duration of response is defined as the time from first documented evidence of CR or PR until disease progression or death due to any cause among subjects who achieve an objective response (ie, CR or PR) as determined by revised response criteria for lymphomas (Cheson et al 2014). For subjects who have not progressed and are still alive at the time of the analysis, DOR will be censored on the day of last evaluable disease assessment. For subjects who have discontinued study or have started other anticancer treatment, DOR will be censored on the day of last evaluable disease assessment documenting absence of PD before the discontinuation or the start of the new anticancer treatment.

Progression-free survival is defined as the time from the date of first dose of the study drug to the first documented disease progression, as determined by revised response criteria for lymphomas (Cheson et al 2014), or death due to any cause, whichever occurs first. For subjects who have not progressed and are still alive at the time of the analysis, PFS will be censored on the day of last evaluable disease assessment. For subjects who have discontinued study or have started other anticancer treatment, PFS will be censored on the day of last evaluable disease assessment documenting absence of PD before the discontinuation or the start of the new anticancer treatment. For subjects who have no baseline or no postbaseline disease assessment, PFS will be censored with censored duration of 1 day.

The Kaplan-Meier estimation of median DOR and PFS as determined by the IRC and its 95% CIs will be provided.

Complete response rate is defined as the percentage of subjects with a CR as determined by revised response criteria for lymphomas (Cheson et al 2014).

The CRR as determined by the IRC and its 95% exact binomial CIs will be calculated.

Overall survival is defined as the time from the date of first dose of study drug to death due to any cause. For subjects who are still alive at the time of the analysis, OS will be censored on the date the subjects is last known to be alive. The Kaplan-Meier estimation of median OS and its 95% CIs will be provided.

Target lesion size is measured by the sum of the product of diameters of all target lesion sizes. Best percentage change in target lesion size from baseline will be summarized descriptively.

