6. STUDY ASSESSMENTS

All study assessments will be performed as indicated in the schedule of assessments (see [Table 6](#)), and all laboratory assessments will be performed as indicated in [Table 7](#). All assessments mandated throughout the study must be performed on a calendar schedule; delays in treatment administration will not delay performance of assessments. By convention, Week 4, Week 8, Week 12, etc, means the completion of 4, 8, or 12 weeks.

[Table 8](#) presents a summary of clinical laboratory analytes to be assessed. The order of assessments is suggested by the order of mention within the schedule. See [Section 7](#) for instructions on each assessment.

Table 6: Schedule of Assessments

Procedure	Section	Screening	Treatment			EOT	Follow-Up		
		Days -28 to -1	Day 1 ^a	Every 4 Weeks Through Week 48 (± 3 Days)	Every 12 Weeks From Week 48 (± 1 Week)		Safety	Disease	Survival
							EOT + 30-35 Days		Every 12 Weeks (± 1 Week)
Informed consent	7.1	X							
Contact IWRS	7.2	X	X	X	X	X			
Inclusion & exclusion criteria	3	X	X						
Demography and medical history	7.3	X							
Prior/concomitant medications	7.4	X	X	X	X	X	X		
AE assessment ^d	7.5.1	X	X	X	X	X	X		
Comprehensive physical exam	7.5.2	X ^e				X			
Disease-specific physical exam	7.5.3		X	X	X		X		
Vital signs	7.5.4	X	X	X	X	X	X		
12-lead ECG	7.5.5	X	X ^f	X ^f	X	X	X		
ECOG performance status	7.5.6	X	X	X	X	X	X		
CT/MRI scan	7.6.1	X		Every 8 weeks through Week 24 (± 1 week), then every 12 weeks through Week 96, then every 24 weeks thereafter until PD				X ^c	
Bone marrow exam	7.6.2	X ^g		X ^h				X ^h	
Prophylactic treatment for PJP	5.6.1			X ⁱ					
Study treatment dispensing	5.1.1		X	X	X				
Study treatment compliance	5.3		X	X	X	X			
INCB050465 administration	5.2.1		X	X	X				
Disease follow-up	6.4.2							X ^c	
Survival follow-up	6.4.3								X ^j

^a All procedures are to be performed before administration of study treatment on Day 1.

^b [REDACTED]

^c Only for subjects who discontinued study treatment for a reason other than disease progression; radiologic imaging [REDACTED].

- ^d Adverse events will be monitored from the time the subject signs the ICF until at least 30 days after the last dose of study treatment. Serious AEs occurring more than 30 days after the last dose of study treatment should be reported to the sponsor or its designee if the investigator suspects a causal relationship to the study treatment. Once detected, AEs should be followed until resolved or judged to be permanent.

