7.4.3. Progression-Free Survival

Progression-free survival is defined as the time from the date of the first dose of the study drug to the first documented disease progression as determined by revised response criteria for lymphomas (Cheson et al 2014), or death due to any cause, whichever occurs first. For response assessed by the IRC, date of disease progression will be provided by the Clinical Reviewer. Censoring for PFS will follow the algorithm outlined in Table 2, which is based on FDA Guidance for Industry: Clinical Trial Endpoints for the Approval of Non-Small Cell Lung Cancer Drugs and Biologics (2015) and Guidance for Industry: Clinical Trial Endpoints for the Approval of Cancer Drugs and Biologics (2018).

Table 2: Evaluation and Censoring of Progression-Free Survival

Situation	Outcome	Date of Progression or Censoring
No baseline tumor assessments	Censored	Day 1
No valid postbaseline response assessments	Censored	Day 1
Progression documented between scheduled response assessments	Progressed	Date of first overall response of PD
No progression	Censored	Date of last valid radiologic assessment (not NE and not missing)
Study discontinuation for undocumented progression	Censored	Date of last valid radiologic assessment (not NE and not missing)
Study discontinuation for toxicity or other reason	Censored	Date of last valid radiologic assessment (not NE and not missing)
New anticancer treatment started	Censored	Date of last valid radiologic assessment (not NE and not missing) on/before starting a new anticancer treatment
Death before first progressive response assessment	Progressed	Date of death
Death between adequate response assessments	Progressed	Date of death
Death or progression after 2 or more missed assessments	Censored	Date of last valid radiologic assessment (not NE and not missing) before the missed assessments

NE = not evaluable.

The total number of participants whose disease progressed as determined by the IRC or who died, and the number of participants censored will be summarized. The Kaplan-Meier estimate of median PFS as determined by the IRC and its 95% CIs will be provided, with the CIs calculated using the generalization of Brookmeyer and Crowley's method (1982) with log-log transformation (Klein and Moeschberger 1997). Progression-free survival rates at 6, 12, 18, 24, and 36 months will also be provided with 95% CIs calculated using Greenwood's formula to estimate the standard error.

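### PFS for a participant who dies with no postbaseline scan: one rule censors at Day 1, another counts the death as an event, and no precedence is stated

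*Protocol*

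**What the plan says.** Protocol 9.4.1.2 counts death from any cause as a PFS event. Its general censoring sentence is limited to subjects who have not progressed and are still alive. The last sentence of the same paragraph has no such limit: "For subjects who have no baseline or no postbaseline disease assessment, PFS will be censored with censored duration of 1 day".

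SAP 7.4.3 keeps the definition that includes death and sends all censoring decisions to Table 2. Four rows matter here:

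| Table 2 row | Outcome | Date |
|---|---|---|
| "No valid postbaseline response assessments" | Censored | Day 1 |
| "Death before first progressive response assessment" | Progressed | Date of death |
| "Death or progression after 2 or more missed assessments" | Censored | Last valid assessment before the missed ones |
| "New anticancer treatment started" | Censored | Last valid assessment on or before the new treatment |

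A further row censors participants with no baseline tumor assessment at Day 1. The text calls the table an algorithm based on regulatory guidance. It does not say that rows are applied in order, or which row wins when two apply. SAP 11.1 lists only the removal of the per-protocol population as a change from the Protocol.

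**The concern.** A participant who takes study drug and dies before the first postbaseline scan, or after missing only that scan, fits both of the first two rows above, and their outcomes are opposite. So does one whose only scan was not evaluable and who then dies, because the SAP row requires a valid assessment.

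Such participants are foreseen. The response-analysis trigger in Protocol 9.4.1.1 waits until all subjects "have reached at least 1 postbaseline disease assessment or have progressed, withdrawn from the study, or died", so it treats death as an alternative to having a postbaseline assessment. The full analysis set takes in everyone with at least one dose, so these participants stay in the PFS analysis.

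Under the Day 1 reading, the earliest deaths leave the risk set as non-events, contrary to the endpoint's own definition. The error has one direction: the PFS curve, the median and the 6- to 36-month rates all come out too high. PFS by IRC and by investigator are exposed, both overall and by regimen. ORR and CRR keep unassessed participants in the denominator, OS counts every death, and a DOR responder has a postbaseline scan by definition, so none of those is affected by this overlap.

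**Working it through.** The plan gives no figure on this point to reproduce. The check is a reading of the rules, followed by an assumption-based sizing.

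**Reading the rules.** Take a treated participant with a baseline scan who dies in Week 5, with no postbaseline scan and no new therapy.

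- Protocol 9.4.1.2, definition: event at death.
- Protocol 9.4.1.2, last sentence on PFS: censored, duration 1 day.
- SAP Table 2, no-valid-postbaseline row: censored, Day 1.
- SAP Table 2, death row: event, date of death.
- SAP Table 2, missed-assessments row: does not apply, since no scan was yet due (Protocol Table 6 puts the first at Week 8, with a window of one week either side).
- SAP 4.1.4 (partial death dates), the crossover sensitivity analysis in 7.4.3, and 11.1 and 11.2: silent on the choice.

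**Sizing if Day 1 censoring is applied.** Let q be the fraction who die unscanned, and S₀(t) the PFS of everyone else.

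- Deaths as events: S(t) = (1−q)·S₀(t) once the early deaths have occurred.
- Deaths censored at Day 1: the estimate is S₀(t) = S(t)/(1−q).
- With exponential PFS, the ratio of the reported to the true median is ln(0.5(1−q))/ln(0.5).

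The documents give no q, so the values below are assumptions. The 12-month PFS of 50% is also assumed.

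| q | Median ratio | 50% reported as |
|---|---|---|
| 1% | 1.0145 | 0.50/0.99 = 50.5% |
| 2% | 1.0291 | 0.50/0.98 = 51.0% |
| 5% | 1.0740 | 0.50/0.95 = 52.6% |

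A simulation (n = 100, assumed median 12 months, unscanned deaths within 56 days, 40,000 runs) gave median ratios of 1.0145, 1.0291 and 1.0742 and the same 12-month values.

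For scale, the 95% CI half-width at 50% and n = 100, ignoring other censoring, is 1.96 × √(0.25/100) = 0.098, or about 10 points.

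**By regimen.** Cohort 2 allocates 60 participants to two regimens, about 30 each if 1:1 (assumed). SAP 11.2 shows that Treatment B was selected, and the 40 additional participants go to the selected regimen, giving about 30 + 40 = 70. Ignoring crossover reassignment, one unscanned death has this effect:

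- Non-selected regimen, q = 1/30 = 3.3%: median ratio 1.0489; 50% becomes 51.7%.
- Selected regimen, q = 1/70 = 1.4%: median ratio 1.021; 50% becomes 50.7%.

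The half-width at n = 30 is 1.96 × √(0.25/30) = 0.179, so the shift is again small beside the sampling error.

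**The case against.** The best answer is that the SAP already shows what it means. Its definition includes death. Table 2 has a row written for deaths. The results text counts "The total number of participants whose disease progressed as determined by the IRC or who died". Censoring rows ordinarily apply to people without an event. A strict top-down reading cannot be intended either, because the no-progression row would then absorb deaths before the death rows were reached. The SAP (Amendment 2, 28 JAN 2021) is also later than Protocol Amendment 7 (30 JAN 2020), so Table 2 is what will be programmed. Entry requires a life expectancy above 3 months, which limits unscanned deaths. The sizing has no documented input, and the endpoint is descriptive.

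Most of this stands, and it is why the point is minor. It does not remove the overlap. The principle that a death overrides censoring is not written down, and Table 2 does not follow it throughout, since deaths after two or more missed assessments are censored. If event coding is intended, the SAP departs from the Protocol's literal sentence and SAP 11.1 does not say so. The guidance cited for Table 2 and the separate output shells might show the intended order, but the SAP text should settle it.

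The number of Day 1-censored participants who died could largely be recovered from the planned PFS and death listings. That helps a reader find the problem afterwards, but it does not fix the rule.

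**Conclusion.** The concern holds, as a minor point. Taken literally, Protocol 9.4.1.2 censors deaths that its own PFS definition counts, and SAP Table 2 gives two opposite outcomes for the same participant without a precedence rule. Confidence is high on that textual overlap. Whether reported PFS is biased depends on the programming: there is no effect if the death row governs, which is the likelier intent. Under literal Day 1 censoring the bias is always upward, by 1/(1−q). For assumed q of 1% to 5%, with exponential PFS and a true 12-month rate of 50%, that is 0.5 to 2.6 percentage points and 1.5% to 7.4% on the median. No conclusion about the primary endpoint is touched.

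**What to change.** - In SAP Table 2, add the qualifier *and no death* to the row for participants without a valid postbaseline assessment.
- State that a death with no valid postbaseline assessment is an event on the date of death, unless the existing row for two or more missed assessments or the row for new anticancer treatment applies. In those two cases give Day 1 as the censoring date, since no postbaseline assessment is available to use.
- Leave the no-baseline row as it is, but say whether it or the death row takes precedence.
- Record the change in SAP 11.1, and align the Protocol sentence at the next amendment.
- Report how many participants were censored at Day 1 and how many of them died.

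The cost is one table edit, one entry in SAP 11.1 and one programming condition. Reported PFS may be slightly less favourable than under the Day 1 reading.

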9.4.1.3. Other Efficacy Analyses

Analyses of ORR, DOR, CRR, and PFS as reported by the investigator will be summarized as described above.

Analyses of ORR, DOR, CRR, PFS as determined by IRC and OS will also be summarized by treatment regimens (A or B) within each cohort.

Health-related quality of life scales as well as change and percentage change from baseline will be summarized descriptively by visit.

9.4.2. Safety Analyses

9.4.2.1. Adverse Events

A TEAE is any AE either reported for the first time or worsening of a pre-existing event after first dose of study drug and within 30 days of the last administration of study drug. Analysis of AEs will be limited to TEAEs, but data listings will include all AEs regardless of their timing to study drug administration. Adverse events will be tabulated by the MedDRA preferred term and system organ class. Severity of AEs will be based on the NCI CTCAE v4.03 using Grades 1 through 5.

The subset of AEs considered by the investigator to have a relationship to study drug will be considered to be treatment-related AEs. If the investigator does not specify the relationship of the AE to study drug, the AE will be considered treatment-related. The incidence of AEs and treatment-related AEs will be tabulated.

Number (%) of subjects reporting any TEAEs, any SAEs, any Grade 3 or 4 TEAEs, any treatment-related TEAEs, any treatment-related SAEs, any treatment-related Grade 3 or 4 TEAEs, any fatal TEAE, and any TEAEs leading to treatment interruption/dose reduction/discontinuation will be summarized and tabulated by system organ class and preferred term.

9.4.2.2. Clinical Laboratory Tests

Laboratory data will be classified into Grades 1 through 4 using CTCAE v4.03 when applicable. The following summaries will be produced for the laboratory data:

- Descriptive statistics of the value and change from baseline at each assessment time will be provided.
- For laboratory parameters that have CTC grading, shift tables will be provided showing change in CTC grade from baseline to the worst grade postbaseline.
- For laboratory parameters where CTC grades are not defined, shift tables from baseline to the worst postbaseline value will be produced using the low/normal/high classifications based on laboratory reference ranges.

Categorical laboratory data will be tabulated by visit at baseline and postbaseline visits when necessary.

